**Table 14-10 Operating characteristics for the six scenarios**

Scenario	Median PFS SOC Arm (months)	Median PFS PDR001 Arm (months)	HR	Type I error/Power	Estimated HR
1	5.5	5.5	1	0.081	0.973
2	5.5	10.0	0.55	0.922	0.509
3	5.5	8.2	0.67	0.727	0.629
4	7.5	7.5	1	0.191	0.894
5	7.5	13.6	0.55	0.911	0.482
6	7.5	12.9	0.67	0.728	0.586

#### **14.4 Appendix 4: Management algorithms**

These general guidelines for management of toxicities ([Postow 2015-supplementary appendix](#)) constitute guidance to the Investigator and may be supplemented by discussions with the Medical Monitor representing the Sponsor. The guidance applies to all immuno-oncology (I-O) agents and regimens.

A general principle is that differential diagnoses should be diligently evaluated according to standard medical practice. Non-inflammatory etiologies should be considered and appropriately treated.

[figure not shown]
Corticosteroids are a primary therapy for immuno-oncology drug-related adverse events. The oral equivalent of the recommended IV doses may be considered for ambulatory patients with low-grade toxicity. The lower bioavailability of oral corticosteroids should be taken into account when switching to the equivalent dose of oral corticosteroids.

Consultation with a medical or surgical specialist, especially prior to an invasive diagnostic or therapeutic procedure, is recommended.

The frequency and severity of the related adverse events covered by these algorithms will depend on the immuno-oncology agent or regimen being used.

## GI Adverse Event Management Algorithm

[figure not shown]
Rule out non-inflammatory causes. If non-inflammatory cause is identified, treat accordingly and continue I-O therapy. Opiates/narcotics may mask symptoms of perforation. Infliximab should not be used in cases of perforation or sepsis.

Patients on IV steroids may be switched to an equivalent dose of oral corticosteroids (e.g. prednisone) at start of tapering or earlier, once sustained clinical improvement is observed. Lower bioavailability of oral corticosteroids should be taken into account when switching to the equivalent dose of oral corticosteroids.

## Renal Adverse Event Management Algorithm

[figure not shown]
Rule out non-inflammatory causes. If non-inflammatory cause, treat accordingly and continue I-O therapy

Patients on IV steroids may be switched to an equivalent dose of oral corticosteroids (e.g. prednisone) at start of tapering or earlier, once sustained clinical improvement is observed. Lower bioavailability of oral corticosteroids should be taken into account when switching to the equivalent dose of oral corticosteroids.

## Pulmonary Adverse Event Management Algorithm

[figure not shown]
Rule out non-inflammatory causes. If non-inflammatory cause, treat accordingly and continue I-O therapy. Evaluate with imaging and pulmonary consultation.

Patients on IV steroids may be switched to an equivalent dose of oral corticosteroids (e.g. prednisone) at start of tapering or earlier, once sustained clinical improvement is observed. Lower bioavailability of oral corticosteroids should be taken into account when switching to the equivalent dose of oral corticosteroids.

## Hepatic Adverse Event Management Algorithm

Rule out non-inflammatory causes. If non-inflammatory cause, treat accordingly and continue I-O therapy. Consider imaging for obstruction.

[figure not shown]
Patients on IV steroids may be switched to an equivalent dose of oral corticosteroids (e.g. prednisone) at start of tapering or earlier, once sustained clinical improvement is observed. Lower bioavailability of oral corticosteroids should be taken into account when switching to the equivalent dose of oral corticosteroids.

\*I-O therapy may be delayed rather than discontinued if AST/ALT ≤ 8 x ULN and T.bili ≤ 5 x ULN.

\*\*The recommended starting dose for grade 4 hepatitis is 2 mg/kg/day methylprednisolone IV.

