#### **6.2.3 Dose modifications and dose delay**

There will be no dose modifications allowed for PDR001.

All dose interruption, delay and discontinuation should be based on the worst preceding toxicity (CTCAE Version v4.03). If a patient experiences a Grade 3 PDR001-related AE, treatment with PDR001 should be interrupted unless otherwise specified in [Table 6-2](#). Refer to [Section 6.2](#) for Management of toxicities and immune related AEs. Following resolution of the toxicity to

Grade 1, patient may resume PDR001 treatment at the same dose level, if there is no evidence of disease progression.

A decision to resume treatment with PDR001 following the occurrence of a Grade 3 AE is at the discretion of the Investigator. If the investigator considers it to be in the patient's best interest to resume therapy before the toxicity has resolved to Grade 1, this may be permitted on a case by case basis, following discussion with Novartis.

If a patient experiences any Grade 4 PDR001-related AE, the treatment should be discontinued unless otherwise specified in [Table 6-2](#).

In case the infusion cannot be administered at the scheduled visit, it has to be administered as soon as possible. If the delay is between 1 and 7 days the procedures at the original schedule visit should be performed. If the delay is longer than 7 days, the procedure of the following visit should be performed.

Patients who missed 2 infusions plus 7 days should be discontinued from the study treatment and enter the Follow-up period. Exceptions may be made on a case by case basis after discussion between Novartis and the Investigator.

Patients who discontinue the study for an AE or clinically significant abnormal laboratory value must be followed as described in [Section 6.2](#).

All changes in study drug administration must be recorded on the Dose Administration Record eCRF.

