#### **6.2.4 Management of toxicities and immune related AEs (irAEs)**

All the patients whose treatment is interrupted or permanently discontinued due to an AE or clinically significant laboratory value, must be followed-up at least once a week (or more frequently if required by institutional practices, or if clinically indicated) for 4 weeks, and subsequently at approximately 4-week intervals, until resolution or stabilization of the event, whichever comes first. Appropriate clinical experts should be consulted as deemed necessary. In case of suspected irAEs, the relevant immunological assessments (e.g. rheumatoid factor, anti-DNA Ab, etc.) should be performed.

Algorithms have been provided to assist investigators in assessing and managing the following groups of irAEs: Gastrointestinal; Renal; Pulmonary; Hepatic; Endocrinopathy; Skin; and Neurological. Management Algorithms can be found in the [Appendix 4](#).

For non- immune related AE as Grade 1 or 2, treatment with PDR001 maintains dose and schedule unless it specifies in the [Table 6-2](#).

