Grade 3 (PLT < 50,000 - 25,000/mm  )	
Dose delay for PDR001-related Grade 3 until resolved to ≤ Grade 1
 
Discontinue for PDR001-related Grade 3 > 7 days or associated with bleeding

Grade 4 (PLT < 25,000/mm  )	Discontinue for PDR001-related Grade 4
Febrile neutropenia	
(ANC < 1.0 x 10  /L, fever ≥ 38.5°C)	
Dose delay for PDR001-related Grade 3 until resolved to ≤ Grade 1
 
Discontinue for PDR001-related Grade 4

Worst toxicity CTCAE Grade (unless otherwise specified)	Recommended dose interruption, delay and discontinuation for PDR001 during a cycle of treatment
Lymphopenia	
Grade 3 (<0.5-0.2 x 10  /L)	Maintain dose and schedule for PDR001-related ≤ Grade 3
Grade 4 (<0.2 x 10  /L)	Dose delay for PDR001-related Grade 4 until resolved to ≤ Grade 3 PDR001-related Grade 4 lymphopenia or leukopenia does not require discontinuation
Renal See Appendix 4 “Renal Adverse Event Management Algorithm” for additional guidance on monitoring and management of any grade events	
Serum creatinine	
Grade 2 (> 1.5 - 3.0 x ULN) or Grade 3 (> 3.0 - 6.0 x ULN)	Dose delay for PDR001-related ≥ Grade 2 until resolved to ≤ Grade 1
Grade 4 (> 6.0 x ULN)	Discontinue for PDR001-related Grade 4
Liver See Appendix 4 “Hepatic Adverse Event Management Algorithm” for additional guidance on monitoring and management of any grade events	
AST or ALT	
Grade 2 (> 3.0 - 5.0 x ULN)	Dose delay for PDR001-related ≥ Grade 2 until resolved to ≤ Grade 1 Discontinue for concurrent AST or ALT >3x ULN and total bilirubin > 2x ULN
Grade 3 (> 5.0 - 20.0 x ULN) or Grade 4 (> 20.0 x ULN)	Discontinue for PDR001-related ≥ Grade 3 or Grade 4
Bilirubin*	
Grade 2 (> 1.5 - 3.0 x ULN)	Dose delay for PDR001-related ≥ Grade 2 until resolved to ≤ Grade 1 Baseline total bilirubin is within normal limits, delay dosing for PDR001-related Grade ≥ 2 toxicity Baseline AST/ALT or total bilirubin in the Grade 1 toxicity requiring dose delays for reasons other than a 2-Grade shift in AST/ALT or total bilirubin may resume treatment in the presence of Grade 2 AST/ALT or total bilirubin
Grade 3 (> 3.0 - 10.0 x ULN) or Grade 4 (> 10.0 x ULN)	Discontinue for PDR001-related ≥ Grade 3 or Grade 4
Asymptomatic amylase and/or lipase elevation**	

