Grade 3 or Grade 4	Discontinue for PDR001-related Grade 3 lasting > 7 days, or PDR001-related Grade 4
Other laboratory adverse events	
Grade 3 or Grade 4	Dose delay for PDR001-related $\geq$ Grade 3 until resolved to $\leq$ Grade 1 Isolated Grade 4 electrolyte imbalances/abnormalities not associated with clinical sequelae and corrected with supplementation/appropriate management within 72hrs of their onset do not require discontinuation.

*Note: If Grade 3 or 4 hyper-bilirubinemia is due to the indirect (non-conjugated) component only, and hemolysis as the etiology has been ruled out as per institutional guidelines (e.g., review of peripheral blood smear and haptoglobin determination), then delay treatment until resolved <math>\leq</math> Grade 1 and continue treatment at the discretion of the investigator.
 
**Note: A CT scan or other imaging study to assess the pancreas, liver, and gallbladder must be performed within 1 week of the first occurrence of any <math>\geq</math> Grade 3 of amylase and/or lipase. If asymptomatic Grade 2 elevations of lipase and/or amylase occur for a second time, patients will be discontinued permanently from study treatment.
 
***Note: antidiarrheal medication is recommended at the first sign of abdominal cramping, loose stools or overt diarrhea.
	

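### For PDR001-related AST/ALT above 5 and up to 8 x ULN with bilirubin up to 5 x ULN, Table 6-2 says stop but the Appendix 4 hepatic footnote allows delay, and no visible text says which applies

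*Protocol*

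**What the plan says.** **Table 6-2, liver rows.** AST or ALT of Grade 3 (above 5 and up to 20 x ULN) or Grade 4 (above 20 x ULN) carries the action "Discontinue for PDR001-related ≥ Grade 3 or Grade 4". The same wording is used for bilirubin of Grade 3 (above 3 and up to 10 x ULN) or Grade 4. The Grade 2 AST/ALT row adds a combined rule: "Discontinue for concurrent AST or ALT >3x ULN and total bilirubin > 2x ULN". One note to the table softens the bilirubin rule. It begins "If Grade 3 or 4 hyper-bilirubinemia is due to the indirect (non-conjugated) component only" and, once hemolysis is excluded, calls for delay until Grade 1 or lower. It does not cover AST/ALT.

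**Link to Appendix 4.** The liver heading of the table refers the reader to the "Hepatic Adverse Event Management Algorithm” for additional guidance on monitoring and management of any grade events".

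**Appendix 4, hepatic algorithm.** The asterisked footnote reads "I-O therapy may be delayed rather than discontinued if AST/ALT ≤ 8 x ULN and T.bili ≤ 5 x ULN". The introduction to the appendix calls its content general guidance and says it covers all immuno-oncology agents.

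**Sections 6.2.3 and 6.2.4.** For a related Grade 3 event, Section 6.2.3 says "treatment with PDR001 should be interrupted unless otherwise specified in" Table 6-2. Section 6.2.4 describes the appendix this way: "Algorithms have been provided to assist investigators in assessing and managing the following groups of irAEs".

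**The concern.** A patient with a related ALT of 6 x ULN and normal bilirubin is to be stopped under one text and may be held and restarted under the other. The reader reaches the second text by following the first text's own cross-reference, so the footnote is not a stray line that sites would overlook.

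The stake is patient safety. A site that follows the footnote could keep on PDR001 a patient whom the table removes for drug-related Grade 3 transaminase elevation. Section 6.2.3 leaves resumption after a Grade 3 event to the investigator and does not always require recovery first: if the investigator wishes to "resume therapy before the toxicity has resolved to Grade 1, this may be permitted on a case by case basis, following discussion with Novartis". Re-exposure could therefore come before the liver values have settled.

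There is a smaller reporting consequence. Protocol Section 12 allows no authorized deviations, and SAP Section 2.4 tabulates patients who stayed on treatment after meeting a withdrawal criterion. Whether a delayed patient belongs in that category could depend on which text governs.

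**Working it through.** The plan states no figure on this point, so there is none to reproduce. The check is an overlap of threshold ranges, in multiples of ULN, for PDR001-related values.

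**Inputs**
- Table 6-2 stop rules: AST/ALT > 5; bilirubin > 3 (unless indirect-only with hemolysis excluded); AST/ALT > 3 together with bilirubin > 2.
- Appendix 4 footnote, delay allowed: AST/ALT ≤ 8 and bilirubin ≤ 5.

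**Overlaps**
- AST/ALT: (> 5) and (≤ 8) gives above 5 and up to 8, with bilirubin ≤ 5.
- Bilirubin: (> 3) and (≤ 5) gives above 3 and up to 5, with AST/ALT ≤ 8. The part not already covered by the first overlap is AST/ALT ≤ 5.
- Combined rule: AST/ALT above 3 and up to 8 with bilirubin above 2 and up to 5. The part not covered by the first two overlaps is AST/ALT above 3 and up to 5 with bilirubin above 2 and up to 3.

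**Test values**

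| AST/ALT, bilirubin (x ULN) | Table 6-2 | Footnote | Result |
|---|---|---|---|
| 5, 1 | delay | may delay | no conflict |
| 5.1, 1; 6, 1; 8, 5 | stop | may delay | clear conflict |
| 6, 4 (indirect-only) | stop, on AST/ALT | may delay | clear conflict |
| 8.1, 1; 9, 2; 6, 6 | stop | does not apply | no conflict |
| 2, 4 (not indirect-only) | stop, on bilirubin | may delay | conditional |
| 4, 2.5 | stop, combined rule | may delay | conditional |
| 2, 4; 2, 5 (indirect-only, hemolysis excluded) | delay | may delay | no conflict |
| 2, 6; 2, 11 (indirect-only, hemolysis excluded) | delay, by the table note | gives no permission | delay rests on the table note alone |

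The conditional rows follow from the footnote's wording, but the flowchart box carrying the asterisk is not visible in the text reviewed, and that box might confine the footnote to AST/ALT-driven stops. The clear zone does not need the figure. The footnote speaks of delay in place of discontinuation, so it modifies a stop instruction, and its AST/ALT limit of 8 lies above the table's stop threshold of 5.

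**Is there a precedence rule?**
- Section 6.2.3 sets Table 6-2 against that section's own defaults (interrupt for Grade 3, discontinue for Grade 4). It does not mention Appendix 4.
- Section 6.2.4 gives the algorithms an assisting role and does not rank them.
- The action column of Table 6-2 is itself headed as a recommendation.
- The introduction to Appendix 4 calls it guidance, yet its scope includes PDR001.

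**Is the footnote an intended exception?** Where the sponsor wanted exceptions, Table 6-2 states them: controlled endocrinopathies, isolated amylase or lipase, isolated electrolyte changes, indirect-only bilirubin. None covers AST/ALT above 5 and up to 8 x ULN.

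**The case against.** The best defence is that the order of authority is clear enough. Section 6.2.1 says the protocol contains specific stopping rules. Section 6.2.3 ties dosing action to Table 6-2 and never names Appendix 4. Section 6.2.4 says the algorithms assist. Appendix 4 is generic, while the table is specific to PDR001, and the liver heading sends the reader there for monitoring and management, not for a dosing rule. The footnote is also only a permission, so a site that stops under Table 6-2 complies with both texts. Early resumption needs discussion with the sponsor, and Section 6.2.4 requires at least weekly follow-up for four weeks after an interruption. Enrolment was complete by August 2018, so few patients remained exposed.

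Most of this stands as an argument about size. It shows that Table 6-2 is the better reading, that safeguards exist and that the practical effect is probably small. It does not remove the conflict: an inference from emphasis is not a stated rule, and a permission to delay contradicts an instruction to stop for any site that uses it. The unseen flowchart limits what can be said about the bilirubin and combined-rule zones, but not about AST/ALT above 5 and up to 8 x ULN.

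It is also fair to say that the conflict could be settled the other way, by writing the delay option into Table 6-2. That would be a clinical decision for the sponsor.

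**Conclusion.** The point holds: the protocol is wrong as written, because two texts give different actions for the same values. The conflict is clear for PDR001-related AST/ALT above 5 and up to 8 x ULN with total bilirubin ≤ 5 x ULN, and confidence is high for that zone only. It extends to bilirubin above 3 and up to 5 x ULN that is not indirect-only, and to the combined AST/ALT and bilirubin rule, if the footnote applies as worded whatever box it is attached to. There is no conflict at AST/ALT above 8 x ULN, or at AST/ALT above 5 with bilirubin above 5 x ULN.

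How many patients this touches is unknown, since the documents give no incidence of these values. The Amendment 06 study status reports 12 patients on PDR001 at 21 May 2019, so remaining exposure was small but not zero. This is a minor safety-consistency correction that should be made. It has no bearing on power, alpha or the primary analysis.

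**What to change.** Delete the asterisked footnote from the Appendix 4 hepatic algorithm, or align its limits with the full set of Table 6-2 liver criteria: AST/ALT, bilirubin, the combined rule and the indirect-only note. This keeps the stricter, drug-specific rule.

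If a precedence sentence is preferred, limit it to the liver, for example: *For PDR001-related hepatic events, the Table 6-2 liver discontinuation criteria apply.* Do not write a general rule that Table 6-2 overrides Appendix 4. It would reach all seven algorithms, whose flowcharts cannot be seen here, and could loosen any that are stricter than the table.

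The cost is one footnote removed or edited, with at most one added sentence. Design, sample size and analysis do not change.

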## Endocrinopathy Management Algorithm

[figure not shown]
Rule out non-inflammatory causes. If non-inflammatory cause, treat accordingly and continue I-O therapy. Consider visual field testing, endocrinology consultation, and imaging.

Patients on IV steroids may be switched to an equivalent dose of oral corticosteroids (e.g. prednisone) at start of tapering or earlier, once sustained clinical improvement is observed. Lower bioavailability of oral corticosteroids should be taken into account when switching to the equivalent dose of oral corticosteroids.

## Skin Adverse Event Management Algorithm

Rule out non-inflammatory causes. If non-inflammatory cause, treat accordingly and continue I-O therapy.

[figure not shown]

Patients on IV steroids may be switched to an equivalent dose of oral corticosteroids (e.g. prednisone) at start of tapering or earlier, once sustained clinical improvement is observed. Lower bioavailability of oral corticosteroids should be taken into account when switching to the equivalent dose of oral corticosteroids.

\*Refer to NCI CTCAE v4 for term-specific grading criteria.

## Neurological Adverse Event Management Algorithm

Rule out non-inflammatory causes. If non-inflammatory cause, treat accordingly and continue I-O therapy.

Patients on IV steroids may be switched to an equivalent dose of oral corticosteroids (e.g. prednisone) at start of tapering or earlier, once sustained clinical improvement is observed. Lower bioavailability of oral corticosteroids should be taken into account when switching to the equivalent dose of oral corticosteroids.

5.1	Baseline.....	29
5.2	Handling of missing and partial dates	30
5.3	Construction of waterfall graphs	32
6	References	32

1 Introduction

This Statistical Analysis Plan (SAP) provides detailed statistical methodology for the analysis of data from study CPDR001X2201 that will be presented in the final Clinical Study Report (CSR). The output shells (in-text and post-text) accompanying this document can be found in the TFL shells document. The specifications for derived variable and datasets can be found in the Programming Datasets Specifications (PDS) document.

[figure not shown]
All changes to the planned analysis described in this document required before or after database lock will be made through an amendment or addendum, respectively. Note that obvious corrections will be made at the time of analysis to address minor formatting or spelling mistakes present in the TFL shells document without the need to amend.

The SAP, TFL shells and PDS documents may also serve as a reference for the creation of any outputs required outside of the CSR, e.g., IB updates, abstracts, posters, presentations, manuscripts and management updates. Data used for these analyses will have a status aligned to the database lock guidance.

1.1 Study design

This is an open-label, multi-center, randomized, controlled phase II study to evaluate the efficacy and safety of PDR001 versus investigator's choice of treatment in patients with moderately differentiated/undifferentiated locally advanced recurrent or metastatic NPC who progressed on or after first-line treatment. Approximately 114 patients will be randomized with a 2:1 randomization ratio of investigational arm (PDR001) vs. control arm (chemotherapy). The randomization will be stratified by disease status (locally advanced recurrent NPC vs. metastatic NPC). Patients in the control arm will be allowed to crossover to PDR001 treatment if they have radiological progression (per RECIST v1.1) documented by an independent central review and discussed with Novartis. The study design is summarized in [Figure 1-1](#).

Figure 1-1 Study Design

*Patients treated with PDR001 will continue treatment until confirmed PD as per irRC.

1.2 Study objectives and endpoints

Objectives and related endpoints are described in [Table 1-1](#) below.

Table 1-1 Objectives and related endpoints

Objective	Endpoint	Analysis
Primary		
To assess the efficacy of PDR001 versus investigator's choice of chemotherapy in patients with moderately differentiated/undifferentiated locally advanced recurrent or metastatic NPC who progressed on or after first-line therapy	Progression free survival (PFS) as per RECIST v1.1 using central assessment	Section 2.6
Secondary		
To evaluate the anti-tumor activity of PDR001 versus investigator's choice of chemotherapy in patients with moderately differentiated/undifferentiated locally advanced recurrent or metastatic NPC who progressed on or after first-line therapy	Overall survival (OS), overall response rate (ORR), duration of response (DOR), time to progression (TTP) and immune related progression free survival (irPFS) as per irRC using central assessment	Section 2.7
To characterize the safety and tolerability of PDR001	Safety: Incidence and severity of adverse events (AEs) and serious adverse events (SAEs), including changes in laboratory parameters, vital signs and electrocardiograms (ECGs)	Section 2.8

Objective	Endpoint	Analysis
To characterize the pharmacokinetic profile of PDR001 (patients in PDR001 arm)	Serum PK parameters (e.g. AUC, Cmax, Tmax, half-life); Serum concentration vs. time profiles	Section 2.9
To assess emergence of anti-PDR001 antibodies following one or more intravenous (i.v.) infusions of PDR001 (patients in PDR001 arm)	Presence and/or concentration of anti-PDR001 antibodies	Section 2.10
To assess potential predictive markers of efficacy of PDR001 in tumor sample (patients in PDR001 arm)	Assess potential associations between expression of PD-L1, CD8, Foxp3 and other immunological markers such as Lymphocyte activation gene-3 (LAG-3), T-cell immunoglobulin domain and mucin domain-3 (TIM-3), with anti-tumor activity	Section 2.10
To assess the pharmacodynamic effect of PDR001 in tumor sample (patients in PDR001 arm)	TIL counts and expression of immune-related genes (RNA/protein in tumor sample)	Section 2.10
To assess the pharmacodynamic effect of PDR001 in peripheral blood (patients in PDR001 arm)	Assess peripheral, soluble ligands and cytokine levels (including but not limited to IFN- γ , TNF- α , IL-6)	Section 2.10

2 Statistical Methods

